## 1 INTRODUCTION

Oral surgical procedures of any kind, from the extraction of a retained third molar to the rigid internal fixation of a mandibular fracture, may cause postoperative complications such as edema, trismus, and pain and interfere with the quality of life of patients. These aspects are important physiological responses but when observed at high intensity and duration, they may harm this critical period of surgical recovery.

No consensus in the literature allows defining a gold-standard protocol as postoperative conduct but most surgeons try to control the complication factors with drug therapies, from analgesics to anti-inflammatory drugs (steroidal or not). Overall, there is an underestimating of non-pharmacological maneuvers such as an effective instruction on the need for absolute rest and oral cavity hygiene, as well as cryotherapy, which is a common approach in the health field although often used empirically. The topical application of ice reduces the temperature of the skin and its adjacent tissues by 2 to 4 cm in depth, resulting in cold-induced neuropraxia and decreasing the threshold of nociceptor activation and the speed of conduction of nerve pain signals. This consequentially reduced blood flow through vasoconstriction, which may decrease the intensity of the inflammatory response of soft tissues to trauma.

The benefits of cryotherapy are not a consensus in the literature and this situation is often justified by the lack of a solid and effective treatment protocol, although the most used approach is applying ice to the region every 30 minutes in the first days. This conflict in the evidence can be seen in publications with results indicating that cryotherapy has no significant influence on edema and trismus, while other aspects report a positive increase in pain relief and other postoperative symptoms. The major unknown is still the actual influence of this therapy on pain levels.

Considering the extensive use of cryotherapy in third molar surgeries and the lack of agreement of scientific findings on its effectiveness, the present study evaluated whether the use of ice has a beneficial potential capable of reducing the intensity and duration of pain, as well as reducing edema and trismus and improve the quality of life.

## 2 OBJECTIVES

### 2.1 GENERAL OBJECTIVE

To investigate the effects of cryotherapy on postoperative outcomes (pain intensity, edema, trismus and quality of life) following mandibular third molar extraction

### 2.2 SPECIFIC OBJECTIVES

- Measure the interincisal distance (in millimeters) on postoperative days 0, 2, and 7.
- Evaluate trismus by measuring the maximum interincisal opening with the patient seated and the tragus–ala plane parallel to the ground, using the average of three consecutive mouth openings.
- Compare the levels of postoperative discomfort associated with anesthetic agents using a visual analog scale (VAS).

## 3 JUSTIFICATION

Cryotherapy with ice is widely used in the postoperative period as a non-pharmacological strategy for controlling these signs and symptoms, due to its potential to reduce local blood flow, inflammatory response, and nerve conduction. However, despite its routine use in clinical practice, there is still controversy in the literature regarding the actual effectiveness of ice application after third molar extraction. Therefore, it is relevant to scientifically evaluate the effects of postoperative cryotherapy following this procedure in order to support evidence-based clinical decisions and optimize postoperative recovery management.

## 4 MATERIALS AND METHODS

The study is designed as a randomized, controlled, split-mouth clinical trial. Patients that don't receive cryotherapy are defined as group A (GA), while patients receiving cryotherapy with ice are classified as group B (GB).

### 4.1 SAMPLE CALCULATION

The sample size was calculated based on a previously published study, which adopted a significance level of 5% ( $p < 0.05$ ), a statistical power of 90%, and a margin of error of 5%, resulting in a required sample size of 40 surgical sites. In the baseline study, pain perception during local anesthesia was compared between acupressure and cryotherapy using a split-mouth design involving 20 patients. Similarly, the present study employed a split-mouth design, with procedures performed on 20 patients, yielding a total of 40 surgical sites.

### 4.2 ETHICAL ASPECTS

The study will be conducted in accordance with the Guidelines and Regulatory Standards of the National Health Council (Resolution No. 466/12), which establishes the ethical guidelines for research involving human subjects in Brazil.

The benefit of participating in the research is indirect, as the patient contributes to the discovery of scientific evidence that will serve as the foundation for safer and more effective treatment.

Patient personal data, collected through direct contact with the participant during the study, will not be disclosed, and confidentiality will be ensured for all participants. This data will be stored in a Google Drive spreadsheet linked to the researchers' institutional email address.

Surgical procedures and the participant's participation in the project may present certain surgical and confidentiality risks inherent to participation, which are outlined in the Informed Consent Form (APPENDIX A).

This study was approved by the Research Ethics Committee of the Faculty of Dentistry and by the CEP (CAAE: 17700019.7.0000.5347) of the Federal University of Rio Grande do Sul (UFRGS; Porto Alegre, RS, Brazil).

### 4.3 TYPE OF STUDY

The study is a randomized, controlled, split-mouth clinical trial.

#### **4.4 SAMPLE**

The sample selection consisted on patients referred to the Federal University of Rio Grande do Sul's Dentistry School. The selected patients require bilateral extraction of lower third molars under local anesthesia in two different surgical times. There will be no change to the routine care for patients volunteering in the study. The surgical procedures will be performed by the research team responsible for this study. Participants of both sexes, aged 18 to 50 years, were included in the study if they presented an indication for bilateral surgical removal of mandibular third molars in similar positions according to Pell and Gregory classification. Additional inclusion criteria comprised the absence of systemic comorbidities, local conditions free of inflammatory or infectious processes, no history of allergy to the prescribed medications, and no recent or chronic use of antibiotics, anti-inflammatory drugs, corticosteroids, or analgesics. Participants were excluded from the study if they used medications other than those prescribed by the surgeon, failed to provide the required data, belonged to Group A (control) but used postoperative ice packs, or belonged to Group B (test) and did not use ice packs as instructed by the researchers. There were three dropouts due to noncompliance with postoperative recommendations and the use of non-prescribed medication, resulting in 34 procedures performed in 17 patients.

Postoperative consultations were conducted for follow-up, suture removal, and the evaluation and treatment of any potential postoperative complications.

The selection of the control group and experimental groups were determined by a simple randomization in the immediate postoperative period. One surgical site didn't receive cryotherapy (GA), while the other site received cryotherapy with ice (GB).

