#### **4.5 SURGICAL TECHNIQUE**

All surgical procedures were performed by a team composed of two trained and calibrated surgeons, exclusively during the morning period. Each patient was treated by the same surgeon for both surgical procedures. A standardized surgical protocol was applied in all cases and included anamnesis, clinical examination, and collection of vital signs (blood pressure and heart rate).

Patients were positioned in the dental chair and underwent antisepsis of the oral cavity and adjacent extraoral region using 0.12% aqueous chlorhexidine. After establishment of a sterile surgical field, local anesthesia was administered via inferior

alveolar, lingual, and buccal nerve blocks using 2% mepivacaine with 1:100,000 epinephrine. A mucoperiosteal incision was made extending from the retromolar area to the mesial aspect of the second molar, with a relaxing incision in an open L-shaped design to expose the underlying bone. Under copious saline irrigation, osteotomy was performed in the distobuccal region using a #6 round bur, and odontosection was carried out when necessary using a 702 surgical bur. Following tooth removal, wound closure was achieved with simple interrupted sutures using 4-0 silk sutures.

Prior to the first surgical procedure, maximum mouth opening was measured in millimeters using a measuring tape to determine the interincisal distance. In cases where maxillary or mandibular incisors were absent, the occlusal edges were used as reference points. This measurement was used as a baseline parameter for comparison between procedures.

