#### **4.6 POSTOPERATIVE CARE**

In the immediate postoperative period following the first surgical procedure, the allocation of postoperative care—with or without cryotherapy—was randomized using a simple draw. Allocation was determined by the selection of a folded paper indicating Group A or Group B and was supervised by a third party to ensure allocation concealment. When the first surgical site of a patient was assigned to Group A (control), the contralateral site in the second surgical procedure was assigned to Group B (test), and vice versa.

Group A (control) did not receive postoperative cryotherapy. Group B (test) was instructed to apply standardized ice packs (11 × 8.5 × 1 cm), provided by the research team, positioned diagonally to cover both the mandibular angle and the cheek on the operated side. Cryotherapy was initiated immediately after surgery under surgeon supervision and continued for the first 12 postoperative hours, consisting of 30-minute applications followed by 30-minute intervals (total of 12 applications). During the intervals, patients were instructed to store the ice packs in a freezer until the next application.

All participants received identical pharmacological postoperative instructions (APPENDIX B) for both interventions, including paracetamol 1 g every 6 hours for 3 days and mouth rinses with 0.12% aqueous chlorhexidine digluconate twice daily for 7 days, starting on the day following surgery. In cases of persistent pain, trismus, or edema that significantly interfered with daily activities despite the use of prescribed analgesics, patients were instructed to use rescue medication consisting of codeine 30 mg every 4 hours as needed.

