## 5.2 TRISMUS

Cryotherapy did not significantly affect maximum mouth opening during the postoperative period ( $F_{(1,16)} = 0.006$ ,  $p = 0.93$ ). However, a significant effect of time ( $F_{(2,32)} = 45.410$ ,  $p < 0.001$ ) and a significant interaction between treatment and time ( $F_{(2,32)} = 4.703$ ,  $p = 0.016$ ) were observed.

Mouth opening decreased on postoperative day 2 compared with baseline in both the control group ( $43.8 \pm 8.9$  vs.  $30.1 \pm 12.2$ ;  $p < 0.001$ ) and the cryotherapy group ( $39.3 \pm 8.8$  vs.  $31.4 \pm 7.9$ ;  $p < 0.01$ ). In Group A, mouth opening remained significantly reduced on postoperative day 7 compared with baseline ( $43.8 \pm 8.9$  vs.  $37.8 \pm 13.6$ ;  $p = 0.005$ ). In contrast, Group B showed recovery of mouth opening by day 7, with values comparable to baseline ( $39.3 \pm 8.8$  vs.  $40.5 \pm 8.5$ ;  $p = 0.43$ ) (Table 2).

[figure not shown]

Table 2: Average of maximal mouth opening values on days 0, 2 and 7 post-op.

Correlation analysis revealed no significant association between pain intensity

and trismus in Group B on postoperative days 2 ( $r = 0.15$ ,  $p = 0.54$ ) or 7 ( $r = 0.11$ ,  $p = 0.66$ ). In contrast, a significant positive correlation was observed in Group A on postoperative day 7 ( $r = 0.62$ ,  $p = 0.005$ ), indicating that greater pain intensity was associated with increased mouth opening restriction. No correlation was found on postoperative day 2 in Group A ( $r = 0.30$ ,  $p = 0.23$ ) (Table 3).

[figure not shown]

Table 3: Correlation between pain and trismus for control group.

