Regarding quality of life, three variables demonstrated notable percentage differences between groups. First, participants in the cryotherapy group reported less difficulty sleeping, likely reflecting the superior pain control achieved with this intervention. Second, when asked which procedure resulted in greater postoperative improvement, all 11 participants who initially underwent the control protocol reported greater improvement following the cryotherapy intervention. Participants described a reduction in burning or heat sensations and perceived a faster recovery trajectory compared with the non-cryotherapy procedure, consistent with the pain outcomes shown in Table 1. Third, patients treated with cryotherapy reported less difficulty opening their mouths, which appears to be closely related to their lower subjective pain perception. As demonstrated in Tables 1 and Graphic 2, the greater reduction in pain intensity in the test group was reflected in a lower proportion of participants reporting functional limitation.

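### No interval or recovery condition separates the two surgeries and the model has no period term, so carry-over cannot be excluded; the single mouth-opening baseline in section 4.5 does not fit the two printed in section 5.2

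*Combined protocol and SAP*

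**What the plan says.** Section 4.4 gives the timing of the two operations in one sentence: "The selected patients require bilateral extraction of lower third molars under local anesthesia in two different surgical times". No minimum or actual interval appears anywhere. The nearest text to a readiness condition is among the inclusion criteria in 4.4: "local conditions free of inflammatory or infectious processes" and "no recent or chronic use of antibiotics, anti-inflammatory drugs, corticosteroids, or analgesics". Nothing says that these are checked again before the second side.

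Section 4.6 draws the care for the first side after the first surgery. If that side is the control, "the contralateral site in the second surgical procedure was assigned to Group B (test), and vice versa". The order that resulted can be read from section 6, which refers to "all 11 participants who initially underwent the control protocol"; section 4.4 gives the total, "resulting in 34 procedures performed in 17 patients".

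On the baseline, section 4.5 states: "Prior to the first surgical procedure, maximum mouth opening was measured in millimeters using a measuring tape to determine the interincisal distance". It adds that this value served as the baseline for comparing the procedures. Section 4.7 lists mouth opening on days 0, 2 and 7, and section 6 speaks of immediate postoperative measurements as the comparator for day 7.

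Section 4.8 specifies a two-way repeated-measures ANOVA with time, treatment and their interaction. It has no term for period or surgery order. Section 5.2 reports: "In Group A, mouth opening remained significantly reduced on postoperative day 7 compared with baseline", and recovery to baseline in Group B.

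**The concern.** A within-patient comparison of two successive operations needs the first to have worn off before the second is measured. Edema is taken from landmarks on one side of the face. Interincisal opening and the questionnaire items on chewing, speech, sleep and daily tasks belong to the whole patient, so anything left over from the first operation enters the second side's data directly. The first operation also brings three days of paracetamol and possibly codeine, which bears on the medication criterion.

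The trial's own figures show that recovery was not complete for everyone when follow-up ended. Control-side opening was reduced at day 7, and difficulty opening the mouth was still reported by 31% in Group A and 23.5% in Group B (section 5.4). Cryotherapy came second in most patients.

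At stake is the conclusion in section 7 that cryotherapy shortens the period of limited opening. The treatment main effect on opening is null (p = 0.93), so this conclusion rests on the treatment-by-time interaction and on each group's change from its own baseline. Both depend on which day-0 reading was used.

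**Working it through.** **Inputs.** Section 5.2: Group A opening 43.8 mm (SD 8.9) at baseline and 37.8 mm at day 7; Group B 39.3 mm (SD 8.8) and 40.5 mm; interaction F(2,32) = 4.703. Section 6: 11 control-first patients. By subtraction, 17 − 11 = 6 were cryotherapy-first; the 83% in section 5.4 agrees with 5/6 = 83.3%.

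**Reported test.** The upper tail of F(2,32) at 4.703 is 0.0162, so the printed 0.016 reproduces. The degrees of freedom are 17 − 1 = 16 for treatment and 2 × 16 = 32 for the interaction. All 17 patients thus contribute both sides, and missing patients do not explain unequal baselines.

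**Baseline conflict.** One reading per patient, used for both sides of the same 17 patients, gives identical means. The printed means differ by 43.8 − 39.3 = 4.5 mm. Either a second reading entered the analysis or a figure is wrong.

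**What carry-over would predict.** Suppose opening was read before each surgery and the first side's day-7 status persisted in full to the second surgery. With T the untouched opening:

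| Assumption | Calculation | Gap A − B (mm) |
|---|---|---|
| Same 6.0 mm deficit after either care | (11 − 6) × 6.0/17 | 1.8 |
| Printed day-7 levels, T = 43.8 | A: (11 × 43.8 + 6 × 40.5)/17 = 42.6; B: (6 × 43.8 + 11 × 37.8)/17 = 39.9 | 2.7 |
| Printed day-7 levels, T = 45.6, solved from A's baseline | 43.8 − (6 × 45.6 + 11 × 37.8)/17 = 43.8 − 40.6 | 3.2 |
| 6.0 mm deficit after control, none after cryotherapy | 11 × 6.0/17 | 3.9 |
| Printed changes: −6.0 after control, +1.2 after cryotherapy | (11 × 6.0 + 6 × 1.2)/17 | 4.3 |

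If only half persisted, the first and the last two rows become 0.9, 1.9 and 2.2 mm. If none persisted, the gap is zero.

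**Chance, given two readings.** The standard error of the gap is √[(8.9² + 8.8² − 2r × 8.9 × 8.8)/17]. The within-patient correlation r is not given. The paired p-value is 0.16 at r = 0, 0.052 at r = 0.5, 0.016 at r = 0.7 and 0.004 at r = 0.8.

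**Effect of the baseline on the result.**
- Own baselines: A 37.8 − 43.8 = −6.0; B 40.5 − 39.3 = +1.2; difference 7.2 mm.
- 43.8 mm for both: A −6.0; B 40.5 − 43.8 = −3.3; difference 2.7 mm.
- 39.3 mm for both: A −1.5; B +1.2; difference 2.7 mm.

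With any common baseline the difference in change equals the day-7 difference, 40.5 − 37.8 = 2.7 mm. The baseline gap supplies the other 4.5/7.2 = 62.5% of the 7.2 mm.

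**Direction.** If a second, depressed baseline was used, regaining it is easier for the care that came second, which was cryotherapy in 11 of 17; the bias favours cryotherapy. If the single baseline was used, each 1 mm of deficit left after control lowers the cryotherapy mean by 11/17 = 0.65 mm, which works against cryotherapy.

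**The case against.** The strongest reply is that section 4.5 documents one baseline, under which carry-over cannot produce a baseline gap at all and would make the favourable day-7 and questionnaire comparisons conservative. That stands as far as section 4.5 goes, but it leaves the two printed baselines unexplained.

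A reader might take the closeness of 4.3 and 4.5 mm as evidence that carry-over happened. The documents do not support this. The 4.3 mm is the top of the range. It needs the day-7 deficit to last undiminished to an unknown date. It also credits cryotherapy-first patients with a 1.2 mm gain (p = 0.43) that, if carry-over occurred, would partly reflect control-first patients recovering from a low start. Chance is not excluded, and section 6 leaves open that day 0 was an immediate postoperative reading.

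There are also partial safeguards. The surgical protocol in 4.5 includes anamnesis and clinical examination in all cases, and 4.4 provides follow-up consultations. Neither sets a threshold, but nothing shows that any patient was operated on again soon after day 7. The equal edema baselines (123.0 and 123.1 mm) neither support nor contradict carry-over in a whole-mouth measure, because edema is measured on one side.

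**Conclusion.** The omission and the baseline conflict both stand. Carry-over into the second side cannot be excluded from the documents, and the passages on the mouth-opening baseline must be reconciled. Carry-over is one possible source of the 4.5 mm gap (1.8 to 4.3 mm predicted with full persistence, less otherwise); chance and a different day-0 reading are others.

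The consequence for the trismus result does not depend on which explanation is right. With a common baseline the between-group difference in change is 2.7 mm rather than 7.2 mm. If that baseline is 43.8 mm, Group B has not regained it by day 7.

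Two further inferences go too far. The figures do not show that cryotherapy has no effect on opening: every prediction above 1.8 mm in the table assumes that control-first patients kept the larger deficit. Nor is the direction of bias settled, since it reverses with the baseline used. For the questionnaire the exposure is a matter of design only; no figures by order are printed. All predictions apply means pooled over both orders to each order, and results by order would be needed to test that.

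**What to change.** For the data in hand:

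1. From the records, report the interval between surgeries and the day-0 opening by surgery order (11 control-first, 6 cryotherapy-first).
2. State which day-0 reading was analysed, when it was taken, and reconcile section 4.5 with 4.7, 5.2 and 6.
3. Repeat the mouth-opening analysis with the pre-first-surgery opening as the common baseline and a period term. Show mouth-opening and questionnaire results by order.
4. If recovery before the second surgery cannot be shown, qualify the trismus and quality-of-life conclusions in sections 6 and 7 as possibly affected by carry-over.

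The protocol should also state the interval or readiness condition that the investigators used or will use, and whether the entry criteria were re-checked. Its content is theirs to set.

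Dropping slow recoverers is not a good substitute: it selects on a result of the first-period care and would tend to remove control-first patients.

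The cost is small. The period term uses one degree of freedom. With an 11/6 split and equal variances, the variance of the treatment difference rises by the factor 17²/(4 × 11 × 6) = 289/264 = 1.09, about 5% on the standard error. A period term does not remove unequal carry-over, and with 11 and 6 patients a test for it would be weak, so items 1 and 2 carry most of the weight.

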#### 4.8 STATISTICAL ANALYSIS

Data normality was assessed using the Kolmogorov–Smirnov test. Parametric analyses were applied to compare groups (control side vs. test side) and postoperative time points (from day 0 to day 7). Continuous variables, including pain intensity (VAS scores), maximum mouth opening (mm), and facial edema (mm), were expressed as means  $\pm$  standard deviation (SD).

A two-way repeated-measures analysis of variance (ANOVA), followed by Fisher's least significant difference (LSD) post hoc test, was used to evaluate the main effects of time and treatment, as well as their interaction, for pain intensity, trismus, and edema. Pain reports were also qualitatively analyzed based on the frequency distribution of pain categories (no pain, mild pain, moderate pain, and severe pain) for both groups.

Associations between pain intensity and trismus or edema were assessed using Pearson's correlation coefficient. Trismus and edema were additionally evaluated using the formulas (Baseline – Postoperative) and (Postoperative – Baseline), respectively. Qualitative data related to quality of life were presented as percentages.

All statistical analyses were performed using SPSS software (version 20.0; IBM Corp., Armonk, NY, USA). Statistical significance was set at  $P < 0.05$ .

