### 5 RESULTS

#### 5.1 POSTOPERATIVE PAIN INTENSITY

The analysis demonstrated significant main effects of treatment ( $F_{(1,16)} = 5.063$ ,  $p = 0.039$ ) and time ( $F_{(7,112)} = 6.254$ ,  $p < 0.001$ ) on postoperative pain intensity (Table 1). Overall, pain scores were higher in Group A than in Group B ( $2.0 \pm 1.2$  vs.  $1.3 \pm 1.1$ ;  $F_{(1,16)} = 5.063$ ,  $p = 0.039$ ).

[figure not shown]

[figure not shown]
Table 1: Average pain levels on every post-operative day for each group. (\*) indicates statistical differences between control and test groups.

In Group A, pain intensity was significantly higher on postoperative days 1 ( $3.59 \pm 0.59$ ;  $p = 0.014$ ) and 3 ( $3.24 \pm 0.55$ ;  $p = 0.005$ ) compared with day 0 ( $1.35 \pm 0.54$ ). No significant differences were observed between day 0 and the remaining postoperative time points ( $p > 0.05$ ).

[figure not shown]
On the test side (Group B), no significant differences in pain intensity were observed between day 0 and any postoperative evaluation ( $p > 0.05$ ), suggesting that cryotherapy effectively prevented postoperative pain exacerbation.

A significant interaction between treatment and time was also observed ( $F_{(7,112)} = 2.689$ ,  $p = 0.013$ ). Pain intensity was higher on postoperative day 1 (Group A:  $3.59 \pm 0.59$  vs. Group B:  $2.12 \pm 0.42$ ;  $p = 0.017$ ) and day 3 (Group A:  $3.24 \pm 0.55$  vs. Group B:  $1.29 \pm 0.33$ ;  $p = 0.007$ ) in the control group compared with the cryotherapy group.

Postoperative pain was absent in 29.4% of control cases and 44.1% of cryotherapy cases. Mild pain was reported by 50.0% of participants in Group A and 47.8% in Group B, whereas moderate pain occurred in 16.9% and 7.4% of cases, respectively. Severe pain was reported by 3.7% of control cases and 0.7% of cryotherapy cases (Graphics 1 and 2).

Graphic 1: Prevalence of reports of moderate to severe pain (4-10 in visual analogic scale) in the total number of reports of pain (1-10 in visual analogic scale) in the control group after day 2 (last day of analgesic medication).

12

Graphic 2: Prevalence of reports of moderate to severe pain (4-10 in visual analogic scale) in the total number of reports of pain (1-10 in visual analogic scale) in the test group after day 2 (last day of analgesic medication).

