## 5.4 QUALITY OF LIFE

Among the 14 items of the OHIP-14 questionnaire, only three showed significant differences between groups. Regarding mouth opening, 31% of participants in Group A still reported difficulty opening the mouth on postoperative day 7, compared with 23.5% in Group B. Concerning sleep disturbances, Group A showed an approximate 40% reduction in complaints between postoperative days 2 and 7, whereas Group B demonstrated a reduction of approximately 66.6%.

When participants were asked which intervention resulted in greater postoperative improvement, all patients who underwent the control protocol in the first surgery (100%) preferred the cryotherapy intervention. Among those who received cryotherapy during the first procedure, 83% also indicated preference for the cryotherapy side.

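### Three patients of an apparent 20 were removed for conduct that can follow the draw, and the 17-patient analysis is neither labelled per-protocol nor backed by an all-randomised analysis

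*Combined protocol and SAP*

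**What the plan says.** Section 4.6 times the draw: "In the immediate postoperative period following the first surgical procedure, the allocation of postoperative care" was decided by drawing a folded paper, and that one draw fixed the care for both surgeries.

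Section 4.4 then lists grounds for removing a patient. The first two are: "Participants were excluded from the study if they used medications other than those prescribed by the surgeon, failed to provide the required data". The others concern allocated care: a patient who "belonged to Group A (control) but used postoperative ice packs, or belonged to Group B (test) and did not use ice packs as instructed". The outcome is reported in the same section: "There were three dropouts due to noncompliance with postoperative recommendations and the use of non-prescribed medication, resulting in 34 procedures performed in 17 patients".

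Section 4.1 gives the only figure for how many entered: "with procedures performed on 20 patients, yielding a total of 40 surgical sites". Section 4.8 specifies a two-way repeated-measures ANOVA. It names no analysis set, no rule for missing data and no per-protocol label. The abstract gives the sample as 17 without mentioning removals. Section 7 states that cryotherapy was effective on pain, with no reference to the patients left out.

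**The concern.** Randomisation supports a comparison of everyone allocated. Once patients are removed for what they did afterwards, the result describes those who followed instructions and supplied their data. Taking a non-prescribed drug, or not keeping to the allocated care, may reflect how the patient felt under one of the two forms of care. If so, removal selects on response.

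A reader of the abstract or conclusion cannot see that this happened. Nor can a reader of Section 4.4 judge its effect: one pooled reason covers all three patients, with no side, no period, and no statement of whether the second surgery took place or any scores were given. The overall pain effect is close enough to 0.05 that three patients out of 20 could matter to its nominal significance.

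**Working it through.** **1. Counts.** 20 (Section 4.1) - 3 (Section 4.4) = 17 patients, and 17 x 2 = 34 procedures. This reproduces Section 4.4. The loss is 3/20 = 15%, if all 20 were drawn. The two sections still need reconciling, because one says procedures were performed on 20 patients and the other counts 34 procedures in 17.

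**2. Number analysed.** Section 5.1 reports F(1,16) = 5.063 for treatment. Error df of 16 means 17 patients, and the F tail gives p = 0.0389 (stated 0.039). The interaction F(7,112) = 2.689 has 7 x 16 = 112 error df and gives p = 0.0130 (stated 0.013). Sections 5.2 and 5.3 also use 16 and 32 error df.

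The pain categories agree. "Postoperative pain was absent in 29.4% of control cases and 44.1% of cryotherapy cases" equals 40/136 and 60/136, where 136 = 17 patients x 8 days. The full sets are 40 + 68 + 23 + 5 = 136 (Group A) and 60 + 65 + 10 + 1 = 136 (Group B). With 20 x 8 = 160 entries, 44.1% cannot occur (70/160 = 43.8%, 71/160 = 44.4%).

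**3. Paired statistics behind the pain main effect.**
- Mean difference, control minus cryotherapy: 2.0 - 1.3 = 0.7 (rounded means).
- t = sqrt(5.063) = 2.250 on 16 df.
- SD of paired differences = 0.7 / 2.250 x sqrt(17) = 1.283.
- 95% CI = 0.7 ± 2.120 x 1.283 / sqrt(17) = 0.04 to 1.36.

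**4. Adding the three back (illustration only).** Their scores are not in the documents. Assume that all three were randomised, gave both sides, and had mean difference d:

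- new mean = (17 x 0.7 + 3d) / 20
- new SS = 16 x 1.283² + 17 x 0.7² + 3d² - 20 x (new mean)², plus 2 x 1.283² if the three also vary with SD 1.283
- t = new mean / sqrt(new SS / 19 / 20), on 19 df

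For d = 0 with no spread: mean = 11.9/20 = 0.595; SS = 26.32 + 8.33 - 7.08 = 27.57; SD = sqrt(27.57/19) = 1.205; t = 0.595 / (1.205 / sqrt(20)) = 2.209; p = 0.040.

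| d | p, three share d | p, three vary with SD 1.28 |
|---|---|---|
| +0.7 | 0.015 | 0.021 |
| 0 | 0.040 | 0.0505 |
| -0.7 | 0.104 | 0.121 |

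Significance is lost at about d = -0.16 with a shared value, and at about d = 0 with own spread. If only one of the three gave both sides (n = 18, 17 df), p = 0.039 at d = 0 and 0.056 at d = -0.7.

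**5. Days 1 and 3.** The differences are 3.59 - 2.12 = 1.47 (p = 0.017) and 3.24 - 1.29 = 1.95 (p = 0.007). Treating these p-values as paired comparisons on 16 df gives t = 2.663 and 3.092, and SD = 2.276 and 2.600. The same calculation tips at d = -1.16 (shared) or -0.90 (own spread) for day 1, and at -2.21 or -1.97 for day 3. Day 3 stays below 0.05 even if the three fully reverse the effect (p = 0.041, or 0.049 with own spread).

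**The case against.** The design gives real protection. Removing a whole patient removes both sides, so patient characteristics cannot become unbalanced between sides. Codeine rescue was prescribed (Section 4.6), so taking it was not use of a non-prescribed drug. Section 5.1 reports rescue use in Group A, so rescue users were retained. Both points stand. They limit selection on pain but do not remove it, because selection on response or adherence can still shift a within-patient contrast.

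Section 4.4 also discloses the rule, the number lost and a reason. That stands too, but the disclosure does not reach the analysis section, the abstract or the conclusion.

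The sensitivity figures rest on invented scores, and the three may not have had both surgeries. This is correct. The figures show only how far the result could move, in either direction; at d = +0.7 the evidence becomes stronger.

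A reader might infer more than the documents support:
- **That the three broke the ice rules, or that they did not.** The pooled reason does not say. The recommendations it refers to may or may not include the ice instruction.
- **That knowledge of the intervention by the evaluator makes the pain result worse here.** Patients completed the pain scale at home (Section 4.7), and nothing links the evaluator to the removals.
- **That every reported figure is on 17.** The 31% in Section 5.4 fits 5/16 and no whole count out of 17. The denominator of the 80% for rescue medication is not given.
- **That the order of surgeries among the 17 shows exclusion bias.** Order is a separate matter, and the removals could have worsened or reduced any imbalance.

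**Conclusion.** The point holds as a fault of analysis set and reporting. The repeated-measures results are a per-protocol comparison of 17 patients without that label. No all-randomised analysis is planned, and the conclusion is unqualified.

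Confidence is high for the exclusion rule, for 17 in the ANOVA outcomes and for the missing analysis. It is moderate for 20 randomised, because that figure comes from the sample-size section.

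It would be tempting to conclude that the removals favoured cryotherapy, or that the pain effect would vanish with all patients included. The documents support neither: no link between the removals and pain is shown, and the direction of any bias is unknown. The overall pain effect is sensitive to plausible values for three patients, with p from 0.015 to 0.12 over the range tried. Day 1 and day 3 are sturdier. All of this depends on the back-calculated SD, the rounded means and the assumption that the three gave both sides. The matter should be fixed, but it does not overturn the pain findings.

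**What to change.** - Leave the Section 4.4 exclusions as written. They record what was done, and rewriting them now would misdescribe the study.
- In Section 4.8, label the 17-patient analysis per-protocol. Add an analysis of all randomised patients by the care allocated to each surgery, using every available observation; for example, a mixed model with a patient random effect, treatment, day and treatment-by-day. Label it post hoc, since results are already reported.
- Reconcile Sections 4.1 and 4.4, and state the confirmed number randomised beside the 17 in the abstract.
- For each of the three, report the reason, the side and the period, and say whether the second surgery took place and which scores exist.
- If the three left no usable data, give a sensitivity range in both directions with its assumptions, and limit the Section 7 conclusion to the patients analysed.

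The labels, the count and the itemised reasons cost almost nothing and are needed in any case. The added analysis costs some data retrieval and one model. A patient with only one surgery adds little to the within-patient contrast, so the gain may be small, and the estimate may be slightly diluted.
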